4.4 EXCLUSION CRITERIA

1. E01 is no longer applicable per amended protocol 05.
2. Histological relapse of the underlying cancer or post-transplant lymphoproliferative disease at the time of screening.
3. Current treatment with ibrutinib. Prior treatment with ibrutinib is allowed with a washout of at least 28 days prior to randomization.
4. Female participant who is pregnant or breastfeeding.
5. History or other evidence of severe illness or any other conditions that would make the participant, in the opinion of the Investigator, unsuitable for the study (such as malabsorption syndromes, poorly controlled psychiatric disease or coronary artery disease).
6. Known active hepatitis B virus (HBV) or hepatitis C virus (HCV) or history of human immunodeficiency virus (HIV).
7. Diagnosed with another malignancy (other than malignancy for which transplant was performed) within 3 years of enrollment, with the exception of:
 - Completely resected basal cell or squamous cell carcinoma of the skin.
 - Carcinoma in situ of the cervix.
 - Resected breast ductal carcinoma in situ.
 - Prostate cancer with Gleason score <6 and stable PSA over 12 months.
8. Has had previous exposure to belumosudil.
9. Known allergy/sensitivity to belumosudil or any other ROCK2 inhibitor.
10. Participant has QTc(F) >480 ms.

11. Participant has FEV1 $\leq 39\%$ or has lung score of 3.
12. Participant considered unlikely to adhere to treatment and / or follow protocol in the opinion of the Investigator.
13. Treatment with any non-GVHD investigational agent, or any investigational device or procedure, within 28 days (or 5 half-lives, whichever is greater) of enrollment.

4.5 PRIOR LINES OF THERAPY

Participants must have previously received at least 2 lines of systemic therapy, and no more than 5 lines of systemic therapy for cGVHD. When documenting prior lines of therapy for cGVHD, the following guidelines should be employed:

- Initiation of one or more new systemic therapies for cGVHD is considered a new line of therapy:
 - If the intention is to initiate more than one agent at the same time, start dates may differ by up to 4 weeks in view of eg, scheduling delays, insurance approval, or obtaining drug.
- Topical agents are not considered a line of therapy.

4.6 SCREENING

The screening period commences once the informed consent form (ICF) or assent form is signed. Adequate time must be allowed for the participant to ask questions and make a voluntary decision. The ICF or assent form must be signed before any study-specific samples are taken or study-specific tests or evaluations are conducted. Documented standard of care assessments performed within 14 days of Cycle 1 Day 1 (C1D1) can be used as screening assessments even if done prior to signing of ICF or assent form.

Data regarding screen-failures will be captured in the electronic data capture (EDC) system.

Screening assessments as summarized in the Schedule of Assessments ([Table 6](#)) will be performed within 14 days of Cycle 1 Day 1.

Study eligibility will be based on satisfying all of the study inclusion and exclusion criteria. Participant eligibility must be confirmed by the Medical Monitor or designee prior to randomization.

Re-screening of participants will be allowed only upon approval of the Medical Monitor. A new consent/assent form must be signed to allow re-screening.

4.7 WITHDRAWAL CRITERIA

Participants will receive belumosudil treatment in 28-day cycles until clinically significant progression of cGVHD (defined as progression requiring addition of new systemic therapy for cGVHD), histologic recurrence of underlying malignancy, unacceptable toxicity, Investigator decision, participant preference / withdrawal of consent, loss to follow-up, sponsor decision, or death (whichever occurs first). Belumosudil treatment failures require discontinuation of study drug.

Participants who experience cGVHD progression as defined by NIH criteria but for whom no new systemic therapy is planned may continue to receive belumosudil and be assessed again at their next cycle. If progression per NIH criteria is not confirmed or no new systemic therapy is planned, participants may continue on belumosudil per investigator discretion until they fulfill one of the criteria requiring discontinuation of study drug.

Taper belumosudil after a sustained response for 6 months and cessation of all other immunosuppressants for at least 3 months, at the Investigator's discretion. The tapering schedule for belumosudil is described in [Section 5.2.1](#).

Participants may be withdrawn from study treatment at any time by the Investigator or the sponsor if it is considered detrimental for the participant to continue in the study. The reason for withdrawal must be captured in the eCRF.

Participants have the right to withdraw from the study at any time and for any reason without prejudice to their future medical care by the physician or at the institution. If the participant wishes to voluntarily withdraw from the study, the physician will consult with the participant regarding procedures for safe withdrawal. Every effort should be made to have such participants attend EOT and 28-day follow up visits. In the instances where a reason for withdrawal of consent/assent is given, this will be captured in the eCRF. Participant data up to withdrawal of consent/assent will be included in the analysis of the study, and where permitted, publicly available data can be included after withdrawal of consent/assent.

If a participant becomes pregnant while on study, belumosudil will be discontinued ([Section 6.4.5](#)).

Under Protocol Amendment 3, all participants (excluding the 20 adolescent participants) that have received at least 6 months of belumosudil treatment or are in long-term follow-up without having a failure-free survival event are expected to end participation in study KD025-213. Participants may continue to participate in study KD025-213 if the Investigative Site is awaiting IRB approval of the KD025-217 rollover study titled: "Extended Treatment and Follow-up of Participants Treated with Belumosudil in Study KD025-208 or Study KD025-213".

4.8 REPLACEMENTS

Randomized participants withdrawn from the study before receiving any study drug will be replaced.

4.8.1 Treatment Discontinuation

Treatment discontinuation reasons include the following:

- Clinically significant cGVHD progression requiring addition of systemic therapy for cGVHD. Of note, clinically significant progression does not necessarily require cGVHD progression as defined by NIH Consensus Criteria. For example, a participant with a score of 3 in a given organ may present with clinically significant progression that warrants urgent intervention even though the NIH score remains unchanged.
- Progression of underlying disease as defined by established disease specific criteria.
- An AE that requires permanent discontinuation of study drug.
- Pregnancy.
- Investigator decision.
- Voluntary discontinuation/ withdrawal from the study treatment by the participant (participant may remain eligible for follow up).
- In case a participant wants to permanently discontinue the treatment (ie, withdrawal of consent for the intervention), the participant will be asked if a final assessment is possible to be performed using the procedure normally planned for the last dosing day (EOT and at 28-day follow up visit) with the IMP prior to consent of the withdrawal. See the SoA ([Section 6.1](#)) for the data to be collected at the time of the study treatment discontinuation, for information on the follow-up, and for any further evaluations that would need to be completed.
- Noncompliance to protocol.
- Participant lost to follow-up.
- Termination of the study by sponsor.
- Participant death.
- Received more than 6 months of belumosudil (this does not apply to the 20 adolescents). Of note, participants may continue to participate in KD025-213 if the Investigative Site is awaiting IRB approval of the KD025-217 rollover study titled: “Extended Treatment and Follow-up of Participants Treated with Belumosudil in Study KD025-208 or Study KD025-213”.

5 STUDY TREATMENT

5.1 INVESTIGATIONAL PRODUCT

Belumosudil (2-(3-(4-(1H-indazol-5-ylamino) quinazolin-2-yl) phenoxy)-N-isopropylacetamide-methane sulfonic acid salt), formerly also known as KD025, is an orally available Rho-associated protein kinase-2 (ROCK2) selective inhibitor. Belumosudil will be provided as 200 mg tablets.

In July 2021, FDA granted approval of belumosudil (REZUROCK) for the treatment of adult and pediatric patients 12 years and older with cGVHD after failure of at least 2 prior lines of systemic therapy and subsequently is commercially available for this indication.

5.2 DOSAGE AND ADMINISTRATION

Eligible participants in this study will be randomized (1:1) to one of two treatment arms:

- Arm A: belumosudil 200 mg QD
- Arm B: belumosudil 200 mg BID

Any adolescent taking a PPI or a strong CYP3A4 inducer will begin C1D1 at the following escalated dose: belumosudil 200 mg BID. On Day 1 of cycles 1, 2, 3, 5, 7 and then every 3 cycles (C10D1, C13D1, etc.), and on scheduled PK and PD sampling days, participants must take their dose of belumosudil at the clinic. On Day 1 of other cycles, belumosudil may be taken at home or in the clinic. Other daily doses will be taken at home and the study drug will be dispensed for home administration (see [Section 6.2.2](#) and [Section 6.2.4](#)).

Participants will be instructed to start a meal within 30 minutes prior to taking their belumosudil treatment.

Additional information on dosage and administration of belumosudil can be found in the KD025-213 Pharmacy Manual.

5.2.1 Belumosudil Tapering Guidance

Tapering of belumosudil is allowed after a sustained response for 6 months and cessation of all other immunosuppressants for at least 3 months, at the Investigator's discretion. The tapering schedule for belumosudil is as follows:

- Arm A (QD): 200 mg QD → 200 mg QOD for 2 cycles → Discontinue
- Arm B (BID): 200 mg BID → 200 mg QD for 2 cycles → 200 mg QOD for 2 cycles → Discontinue

Similarly, participants whose cGVHD has not progressed at the time of discontinuation of belumosudil treatment ([Section 4.7](#)) and who come off study for reasons other than AEs should be tapered off belumosudil by reducing the dose every 2 cycles as described above.

5.3 TREATMENT ASSIGNMENT

Eligible participants will be randomized and assigned to a treatment arm (A or B) in this open label, randomized study in accordance with the randomization schedule.

Randomization will be stratified according to:

- Prior ibrutinib therapy (yes/no).
- Severe cGVHD (yes/no) where severe cGVHD is defined as at least one organ with a score of 3, or a lung score of 2 or 3 ([Table 1](#)) ([26](#)).

The randomization will be a block randomization with a block size of 4.

Table 1 - cGVHD Severity Definitions

cGVHD Severity	Definition
Mild cGVHD	1 or 2 organs involved with no more than score 1 plus Lung score 0
Moderate cGVHD	3 or more organs involved with no more than score 1 OR At least 1 organ (not lung) with a score of 2 OR Lung score 1
Severe cGVHD	At least 1 organ with a score of 3 OR Lung score of 2 or 3

Key points:

1. In skin: higher of the two scores to be used for calculating global severity.
2. In lung: FEV₁ is used instead of clinical score for calculating global severity.
3. If the entire abnormality in an organ is noted to be unequivocally explained by a non-GVHD documented cause, that organ is not included for calculation of the global severity.
4. If the abnormality in an organ is attributed to multifactorial causes (GVHD plus other causes) the scored organ will be used for calculation of the global severity regardless of the contributing causes (no downgrading of organ severity score).

Reference: Jagasia et al. ([26](#))

5.4 BLINDING

This is an open-label study.

5.5 TREATMENT COMPLIANCE

Participants will be given a study drug diary to record the details of each dose of study drug.

5.6 MISSED DOSES

Participants should make every effort to take the study drug at the same time every day with their morning/evening meal. Participants will be instructed to start a meal within 30 minutes prior to taking their belumosudil treatment. In the event that the participant misses the planned dose of study drug, the following protocol should be followed:

For participants in Arm A, receiving study drug on a QD dosing schedule:

- If less than 12 hours of time have elapsed after the scheduled dose, the drug should be taken. The participant should then resume the regular planned daily dosing schedule the following day.
- If more than 12 hours of time have elapsed after the scheduled dose, the drug should be skipped for that day. The participant should then resume the regular planned dosing schedule the following day.

For participants in Arm B, receiving study drug on a BID dosing schedule:

- If less than 6 hours of time have elapsed after the scheduled dose, the drug should be taken. The participant should then resume the regular planned dosing schedule.
- If more than 6 hours of time have elapsed after the scheduled dose, the dose should be skipped and the participant should resume dosing with the next the regular planned dose.

If the participant skips more than 7 consecutive days of drug, the participant should be discontinued from the study unless approved by the Medical Monitor and Investigator.

In the event of vomiting, the participant should report the AE and should not take additional doses of study drug to compensate.

5.7 PRODUCT ACCOUNTABILITY

In accordance with regulatory requirements, study sites must document the amount of investigational product received from and returned to the sponsor, and the amounts of investigational product dispensed to study participants, and the amount returned by study participants. Product accountability records must be maintained throughout the course of the study.

5.8 CONCOMITANT MEDICATIONS AND PROCEDURES

All concomitant medications including dietary / herbal / over the counter supplements taken during the study and relevant procedures will be recorded. Initiation of new systemic cGVHD therapy will be considered a new line of treatment and a belumosudil treatment failure; this necessitates discontinuing from study drug.

5.8.1 Corticosteroids

Corticosteroid dose data will be collected throughout the study. Corticosteroids may be tapered at the discretion of the Investigator after ≥ 2 weeks of belumosudil administration.

Transient increases in corticosteroid dosing (not exceeding 1mg/kg/day prednisone equivalent, [Appendix K](#)) are permitted for the treatment of cGVHD flare, but dose must be reduced back to the pre-randomization dose within 6 weeks. If the dose remains elevated for more than 6 weeks, this will be considered a belumosudil treatment failure. More than 2 episodes of cGVHD flare requiring increased corticosteroid therapy in the first 6 months of belumosudil treatment will also be considered a belumosudil treatment failure; this necessitates discontinuing from study drug.

Response assessments scheduled to occur during treatment of a cGVHD flare will be conducted as planned but will not be included in the primary efficacy analysis.

PD samples should be collected at time corticosteroid dose is increased. Refer to the Laboratory Manual for detailed instructions.

5.8.2 Systemic cGVHD Therapies

Per the eligibility criteria, participants receiving standard of care systemic cGVHD therapies such as calcineurin inhibitors (tacrolimus, cyclosporine), sirolimus, MMF, methotrexate, rituximab or ECP, may be enrolled if they have been on a stable dose / schedule. Changes in doses of drugs to maintain therapeutic levels are not considered as a change in dose/schedule.

Doses and schedules of these therapies will be collected throughout the study and changes will be documented.

Doses may be tapered at the discretion of the Investigator after ≥ 4 weeks of belumosudil administration.

Increases in dosage to above the baseline dose are not permitted. An exception is for dose adjustments to maintain therapeutic drug levels.

5.8.3 Topical / Organ Specific Therapies for cGVHD

Use of topical / organ specific therapies for cGVHD is permitted and must be documented.

5.8.4 CYP3A4 Inducers and Proton Pump Inhibitor

Use of strong CYP3A4 inducers decreases belumosudil exposure ([Section 21.9 Appendix I](#)). Use of PPIs (eg, omeprazole [Prilosec], esomeprazole [Nexium], lansoprazole [Prevacid], rabeprazole [AcipHex], pantoprazole [Protonix]) decreases belumosudil exposure. Participants on strong CYP3A4 inducers or PPIs can dose modify to 200 mg BID if they are dosing at 200 mg QD at the Investigator's discretion.

5.8.5 Prohibited Concomitant Medications

Treatment with investigational systemic immunosuppressant drugs for cGVHD is prohibited. Concomitant use of Ruxolitinib is prohibited.

5.9 TREATMENT OF OVERDOSE

Any dose of belumosudil >1000 mg within a 24-hour period will be considered an overdose. In clinical studies of belumosudil, repeat dosing of 500 mg BID for 28 days was generally well tolerated in healthy volunteers. There are no known antidotes to belumosudil, and no specific treatment is recommended in the event of a suspected overdose. The treating Investigator should employ clinical judgment in managing participants with suspected overdose. Overdose should be reported as an AE (Section 9.2).

5.10 DOSE MODIFICATION GUIDELINES

Any clinically significant toxicity will necessitate consideration of either a pause or cessation of therapy. Guidelines for management of treatment-emergent toxicities in participants receiving belumosudil are outlined in [Table 2](#) below.

Table 2 - Guidelines for Management of Treatment-Emergent Toxicities

Toxicity	Recommended Action
ALT or AST increased (more than 20x ULN), blood bilirubin increased (more than 3x ULN) considered at least possibly related to belumosudil	Discontinue belumosudil
Other Grade 4 organ toxicities considered at least possibly related to belumosudil	
Discontinue belumosudil
AST or ALT increased (5x to 20x ULN) or total bilirubin increased (1.5x to 3x ULN) considered at least possibly related to belumosudil	
Hold belumosudil dosing until recovery of total bilirubin (\leq1.5x ULN), AST and ALT (\leq3x ULN), then consider resuming belumosudil at the recommended doseComplete the "Treatment Emergent LFT Elevations" eCRFConsider resuming belumosudil. If resuming, then resume at the recommended doseIf toxicity recurs, discontinue belumosudil
Other Grade \geq 3 clinically significant toxicities considered at least possibly related to belumosudil	
Hold belumosudil dosing until toxicity has resolved to Grade 1 or below then consider resuming belumosudil. If resuming, then resume at the recommended doseIf toxicity recurs, hold dose as above then consider resuming belumosudil at the recommended dose

Abbreviations: ALT=alanine aminotransferase; AST=aspartate aminotransferase; eCRF=electronic case report form; LFT=liver function enzymes.

Dose interruption for up to 14 days for toxicity management is permitted. Participants requiring pauses of more than 14 days will be discontinued from the study unless approved by the Medical Monitor.

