This study uses the Clinician-Reported Global cGVHD Activity Assessment to evaluate cGVHD global severity rating along with other organ severities; the cGVHD Activity Assessment Patient Self Report to assess symptom activity ([Appendix F](#)) and evaluates failure-free survival (FFS).

Full PK profiles will be collected for a subset of approximately 12 participants per arm, and sparse PK sampling will be conducted for the entire study population including adolescent participants.

As exploratory endpoints, changes in the PROMIS Global Health score and changes in relevant biomarkers after belumosudil administration will be explored.

All AEs will be followed for 28 additional days after discontinuation of belumosudil treatment. All SAEs and treatment-related AEs will be followed until either resolution of the event or determination by the Investigator that the event has become stable or irreversible.

In addition, after discontinuation of belumosudil treatment, participants will be contacted every 12 weeks until a failure-free survival event occurs or until study close-out (whichever occurs first) to allow follow up for FFS and survival status.

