3.3 ESTIMATED STUDY DURATION

The study enrollment period is expected to be approximately 24 months.

Individual participant duration on study will consist of up to 2 weeks for screening, treatment until progression of disease ([Section 4.7](#)), and 4 weeks of post treatment follow-up.

In addition, after discontinuation of belumosudil treatment, participants will be contacted every 12 weeks until a failure-free survival event occurs or until study close-out (whichever occurs first) to allow follow up for FFS and survival status.

Study close out is anticipated to occur within approximately 4 years after the first participant is enrolled.

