6.2.8 Long-Term Follow-Up

After the follow-up visit is completed, participants will be contacted approximately every 12 weeks eg, by telephone, e-mail, or postal mail until a failure-free survival event occurs or until the study close-out (whichever occurs first) to confirm survival status, any changes in treatment for cGVHD and the initiation of treatment for the underlying disease. Alternatively, this information may be derived from medical records.

With Protocol Amendment 3, all participants that have not yet had a failure free survival event will end participation with KD025-213. Participants may continue to participate in KD025-213 if the Investigative Site is awaiting IRB approval of the KD025-217 rollover study titled: "Extended Treatment and Follow-up of Participants Treated with Belumosudil in Study KD025-208 or Study KD025-213".

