21 APPENDICES

21.1 APPENDIX A: SCHEDULE OF ASSESSMENTS

Table 6 - Schedule of Assessments

Assessment	Screening	Baseline ^k	Cycle 1 Day 15	28-Day Treatment Cycles ^l	End of Treatment (EOT)	28-Day Follow-Up (±7 days)	Long Term Follow-Up (LTFU)
Cycle Day	-14 to -1	C1D1	C1D15 (±3 days)	CxD1 (±3 days)			
Written Informed Consent/Assent	X ^a						
Participant Demography	X						
Medical History	X						
Transplant History	X						
GVHD History	X						
cGVHD Prior Treatments	X						
Inclusion/Exclusion Criteria	X						
cGVHD severity assessment	X						
Randomization ^b		X					
Efficacy Assessments							
Clinician-reported global cGVHD activity assessment		X		X	X		
Response Assessment				X	X		
Pulmonary Function Tests ^c	X	X		X	X		
cGVHD Activity Assessment - Patient Self Report		X		X	X		
Lee Symptom Scale Score		X		X	X		
PROMIS Global Health Score		X		X	X		
Document Corticosteroid Dosage	Corticosteroid dosage to be collected from the date the ICF/assent form is signed until 28 days after last dose of study drug						
Document other cGVHD therapies	Other cGVHD therapies to be collected from the date the ICF/assent form is signed until 28 days after last dose of study drug						

Assessment	Screening	Baseline ^k	Cycle 1 Day 15	28-Day Treatment Cycles ^l	End of Treatment (EOT)	28-Day Follow-Up (±7 days)	Long Term Follow-Up (LTFU)
Cycle Day	-14 to -1	C1D1	C1D15 (±3 days)	CxD1 (±3 days)			
Follow-Up Contact ^d							X
New Treatment for cGVHD or underlying disease							X
Safety Assessments							
Complete PE ^e	X						
Symptom directed PE		X	X	X	X	X	
Vital signs ^f	X	X	X	X	X	X	
Weight	X	X	X	X	X		
Karnofsky / Lansky Performance Scale score	X	X		X	X	X	
Hematology	X	X	X	X	X	X	
Clinical Chemistry	X	X	X	X	X	X	
Virology ^g	X						
12-Lead ECG ^h (Table 10)	X ^h	X ^h		X ^h	X ^h	X ^h	
Highly sensitive urine or serum pregnancy test ⁱ	X	X		X	X	X	
Concomitant medications / procedures	Concomitant medications / procedures to be collected from the date the ICF/assent form is signed until 28 days after last dose of study drug.						
Adverse events	AEs to be collected from the date the ICF/assent form is signed until 28 days after last dose of study drug.						
Investigational Product							
Study drug administration		X ^j	X ^j	X ^j			
Dispense/Collect Study Drug & Study Drug Diary		X		X	X		
Pharmacokinetics	See Table 7 Table 7 and Table 8						
Pharmacodynamics	See Table 9						

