cGVHD = chronic graft versus host disease; ECG = electrocardiogram; ICF = informed consent form; ECP = Extracorporeal Photopheresis; PE = Physical Examination

a The informed consent/assent form must be signed before any study procedures begin. Documented standard of care assessments performed within 14 days of C1D1 can be used as screening assessments even if done prior to signing of ICF/assent form.

b Randomization after eligibility for the study is confirmed by the Medical Monitor or designee. Randomization may occur during screening or pre-dose on C1D1.

Assessment	Screening	Baseline ^k	Cycle 1 Day 15	28-Day Treatment Cycles ^l	End of Treatment (EOT)	28-Day Follow-Up (±7 days)	Long Term Follow-Up (LTFU)
Cycle Day	-14 to -1	C1D1	C1D15 (±3 days)	CxD1 (±3 days)			

c Lung function assessment to be conducted at time of response assessments (see item d below). Pulmonary Function Tests (PFTs), to include FEV₁, FVC, DL_{CO} (corrected for Hb), TLC, and RV, will be performed at baseline (within 7 days of C1D1 or on C1D1) and Day 1 of Cycles 3, 7, 13 and every 6th Cycle thereafter. During screening, and on Day 1 of other cycles with response assessments, spirometry (FEV₁ and FVC) is sufficient ([Appendix J](#))

d Participants are to be contacted eg. by telephone, e-mail, or postal mail approximately every 12 weeks until a failure-free survival event occurs or until study close-out (whichever comes first) to confirm survival status, any changes in treatment for cGVHD, and the initiation of any anti-cancer treatment.

e Including height. Note that for adolescents (12 – 17 years old) height is also to be assessed at Day 1 of Cycles 1 (ie, baseline), 2, 3, 5, 7, and then at every other 3 treatment cycles.

f Vital sign measurements (sitting blood pressure and heart rate to be obtained after 5 minutes of rest), and respiratory rate and temperature

g Virology to include testing for Hepatitis B and Hepatitis C

h ECGs – see [Table 10](#)

i Females of childbearing potential must have a negative urine pregnancy test. Positive results are to be confirmed with serum testing

j On Day 1 of Cycles 1, 2, 3, 5, 7, and then every 3 cycles (C10D1, C13D1, etc.) and on scheduled PK and PD sampling days, participants must take their dose of belumosudil at the clinic. From Cycle 8 onwards, the Day 1 dose may be taken at home or in the clinic

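### Protocol 5.6 and 5.10 remove participants with long dose gaps from the study, which conflicts with the 12-weekly follow-up required after belumosudil stops; study drug was probably meant, but neither section says so

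*Protocol*

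**What the plan says.** Two operative rules tie a long dose gap to leaving the study.

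- Protocol 5.10, toxicity pauses: "Participants requiring pauses of more than 14 days will be discontinued from the study unless approved by the Medical Monitor".
- Protocol 5.6, more than 7 consecutive days skipped: "the participant should be discontinued from the study unless approved by the Medical Monitor and Investigator".

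Four places require follow-up after treatment ends. None makes an exception for the reason treatment stopped.

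- Protocol 3.1: "after discontinuation of belumosudil treatment, participants will be contacted every 12 weeks until a failure-free survival event occurs or until study close-out". Section 3.3 repeats this.
- Protocol 6.2.8: "After the follow-up visit is completed, participants will be contacted approximately every 12 weeks".
- Table 6 footnote d: "Participants are to be contacted eg. by telephone, e-mail, or postal mail approximately every 12 weeks until a failure-free survival event occurs".

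SAP 3.8.2.5 (TTNT) and 3.8.2.8 (FFS) censor at the later of the last response assessment and the last long-term follow-up assessment, where available.

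**The concern.** A participant stopped for a long gap cannot both leave the study and go on being contacted every 12 weeks. A site that applies 5.6 or 5.10 as worded, without a waiver, would end long-term follow-up. TTNT and FFS for that person would then be censored at the last response assessment.

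These exits are triggered by toxicity or non-adherence. If such participants fail sooner than the rest, the censoring is informative and the FFS and TTNT curves come out slightly too favourable.

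**Working it through.** **Text comparison.** Where only treatment ends, the protocol elsewhere names the drug: 4.7, 5.8 and 5.8.1 all speak of discontinuing study drug. Section 17.4 treats stopping treatment and terminating from the study as separate events. A reader could therefore take the different wording in 5.6 and 5.10 as deliberate.

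Other text points the opposite way. Section 5.10 opens by speaking of pausing or ceasing therapy, and its Table 2 tells sites to discontinue belumosudil. Section 4.8.1 lists "An AE that requires permanent discontinuation of study drug" and noncompliance as reasons for treatment discontinuation. Usage is also loose elsewhere: the synopsis lists AEs leading to study discontinuation where SAP 3.11.1 has study drug discontinuation, and 5.2.1 tapers participants who come off study. However, 4.8.1 mentions remaining eligible for follow-up only for voluntary discontinuation, and neither 5.6 nor 5.10 refers to 4.8.1 or 6.2.8.

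**What would be lost.** Table 6 limits the loss: "Other cGVHD therapies to be collected from the date the ICF/assent form is signed until 28 days after last dose of study drug". New systemic therapy is therefore still captured to day 28, and only later events disappear. The 28-day visit (6.2.6) has no response assessment. Without long-term follow-up, an event-free leaver is censored under the SAP at EOT (due within 7 days of last dose) or earlier.

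**Illustrative size.** The plan gives no figure to reproduce and no rate of such gaps. The nearest rates come from KD025-208: 4% withdrawal due to related AEs (Protocol 10) and about 6% dropout (SAP 3.1). Neither measures this event, and the 6% excludes related AEs by definition.

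Assumptions, none from the documents:

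- exponential failure, with 12-month FFS of 50% in those who stay, so λ = ln 2 / 12 per month;
- a share p of leavers with hazard ratio HR;
- exit uniform over months 0 to 6, at the last dose;
- no waivers.

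FFS with full follow-up = (1 − p) × 0.50 + p × 0.50^HR. For p = 6% and HR 2 this is 0.94 × 0.50 + 0.06 × 0.25 = 0.485.

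Reported FFS = exp(−∫ h(t) dt) from 0 to 12 months, where

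h(t) = λ[(1 − p)e^(−λt) + HR·p·e^(−HR·λt)·G(t)] / [(1 − p)e^(−λt) + p·e^(−HR·λt)·G(t)]

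and G(t) is the share of leavers not yet censored by exit. With loss at exit, G(t) = 1 − t/6 up to month 6 and 0 after that. The last column below was simulated: events count to 28 days after exit, and leavers without an event are otherwise censored 7 days after exit, as the SAP rule implies when the EOT visit takes place.

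Overstatement of 12-month FFS in percentage points, HR 2:

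| Leaving | FFS, full follow-up | Loss at exit | Censored 28 days after exit | SAP rule |
|---|---|---|---|---|
| 4% | 49.0% | +0.7 | +0.6 | +0.5 |
| 6% | 48.5% | +1.0 | +0.9 | +0.8 |
| 10% | 47.5% | +1.7 | +1.5 | +1.3 |

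At HR 1 the first two rules give zero. The SAP rule gives about −0.1 to −0.2, because events are counted to day 28 while event-free leavers drop out of the risk set at day 7.

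For scale, the standard error of a 50% proportion is √(0.25/63) = 6.3 points for one arm of 63, and √(0.25/20) = 11.2 points for the 20 adolescents. One adolescent leaver (5%) at HR 2 shifts FFS by about 0.7 to 0.9 points.

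**The case against.** The strongest reply is that the documents already settle the meaning. Section 5.10 is about dosing, its table speaks of stopping belumosudil, and 4.8.1 classes these reasons as treatment discontinuation. A site could end follow-up only by ignoring four other provisions that are equally explicit. Both rules can be waived, and 5.6 says only that the participant should be discontinued. Section 6.2.8 lets long-term information come from medical records, and 4.7 asks for every effort to obtain EOT and 28-day visits even from participants who withdraw from the study voluntarily.

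Scope is also narrow. Amendment 3 text in 3.1 and 4.7 ends participation for most others and exempts the 20 adolescents (6.2.8 does not repeat that exemption). Rewording now cannot change follow-up of the cohort on which approval was based.

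Most of this stands and sets the weight of the point. The size calculation is illustrative only: every input is assumed, and the answer depends on the censoring date. The model also places exit at the last dose, whereas exit follows more than 14 days (5.10) or 7 days (5.6) without drug. What the reply does not remove is the conflict itself. A site following 3.1 must depart from the words of 5.10, and nothing in 5.6 or 5.10 tells it to.

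Two stronger inferences are tempting. One is that the plan intends to abandon follow-up of participants with toxicity; the context just described points away from that. The other is that the headline result is biased; ORR does not use long-term contacts.

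**Conclusion.** A minor internal inconsistency that is worth correcting. On the literal reading, participants with unwaived long gaps lose long-term follow-up, and their TTNT and FFS are censored for a possibly informative reason. The effect is small and cannot be estimated from the documents. Under the stated assumptions (50% FFS, HR 2, 4% to 10% leaving) it is roughly 0.5 to 1.7 points on 12-month FFS, depending on the censoring date, and about zero or slightly negative at HR 1.

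SAP 3.2 makes these endpoints descriptive only. ORR, alpha and sample size do not change, and the AE and SAE follow-up duties in 3.1, 9.3.2.1 and 9.3.2.3 apply regardless. I make no claim for overall survival: planned contact stops at an FFS event in any case. Under the current version the point concerns chiefly the 20 adolescents.

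**What to change.** In 5.6 and 5.10, have the participant discontinued from *study drug* instead of from *the study*. Add one sentence: the EOT visit, the 28-day visit and long-term follow-up under 6.2.8 continue unless consent to follow-up is withdrawn or participation ends under Amendment 3. Leave the 7-day and 14-day limits and the waivers as they are.

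The cost is one phrase in each of two sections, one cross-reference sentence and a few extra follow-up contacts, mostly among the adolescents.
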